Participants randomized to the MIAPP intervention will utilize their personal smartphones or tablets, or be provided with a smartphone for use during the study period if they do not have access to a personal device or choose not to use their personal device. The patient navigator or other research staff will help patients obtain a study phone when needed. Phones will be returned at the end of the study period. Participants needing a study phone will sign two copies of a [Phone Agreement Contract](#). If the study phone is lost, damaged, or stolen, there is no penalty to the participant; the study phone will be replaced up to one time. If the second phone is lost, damaged, or stolen, participants can continue to upload videos using a personal device if able and willing. Alternatively, they can continue participating in all remaining study procedures without uploading videos – i.e., they can receive a financial reward for linking to an outpatient buprenorphine provider, and they can complete the 30-day follow-up assessment. Participants who choose to utilize their own device will not be reimbursed for data plan costs and will utilize their device's memory.

Protection of Human Subjects

Involvement of Human Subjects

This study will conduct a randomized controlled trial of 40 participants with opioid and methamphetamine use at Harborview Medical Center (HMC) who are initiated on buprenorphine while in the hospital to determine effects of the intervention on post-discharge outcomes of linkage to outpatient treatment, retention on medication, use of opioids or methamphetamine, and hospital

readmissions and ED visits. Patients will be assigned to one of two arms (20 per arm) using a stratified randomization procedure.

Research Material Obtained from Participants

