Descriptive statistics will be calculated for all baseline variables; variables will be assessed for any differences between the two randomized arms using chi-square tests, t-tests, or the Mann-Whitney U test depending on the distributions. Baseline variables that differ between the two arms and potentially confound tests of intervention effects will be included in analyses as covariates. This study will use an intent-to-treat analysis including all subjects according to their randomized assignment, regardless of their follow-up status and their level of compliance with intervention components. The investigators will provide regular written reports to the Data Safety Monitoring Board including outcome data by the unblinded treatment group.

Primary Outcome Analyses

We hypothesize that participants randomized to MIAPP + treatment as usual compared to treatment as usual alone will be more likely to link to outpatient treatment with medications for OUD within the 30 days of hospital discharge. To evaluate the primary hypothesis, we will use modified Poisson regression analysis (53) with robust standard errors to compare intervention arms on the proportion of participants who link to outpatient treatment with medications for OUD within 30 days of hospital discharge, while potentially controlling for any baseline variables that differ between the two groups as described above if they could confound the hypothesis test. The results of this analysis will be presented as the proportion of patients in each group who link to outpatient treatment and the (adjusted) risk ratio (RR, i.e., ratio of the two proportions) with a 95% confidence interval computed by exponentially transforming the coefficient of the treatment effect in the modified Poisson regression model. We will also report the difference between proportions with a 95% confidence interval, as recommended by CONSORT guidelines (54). The RR and difference are two different ways of quantifying the intervention effect that have meaningful clinical interpretations. Results from the Poisson regression will be used for primary interpretation and conclusions.

Secondary Outcome Analyses

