We hypothesize that participants randomized to MIAPP + treatment as usual compared to treatment as usual alone will a) have more days of medications for OUD treatment within the 90 days post-discharge (secondary), b) have lower rates of readmissions to the hospital and emergency department visits within 90 days (exploratory), and c) have fewer days using opioids or methamphetamine 30 days post-hospital discharge (exploratory). Analyses of secondary outcomes will use modified Poisson regression similar to those described above for binary outcomes (readmissions to hospital and emergency department) and linear regression for continuous outcomes (e.g., days of medications for OUD treatment; days of opioid or methamphetamine use).

Sample Size and Power

The primary goal of this pilot trial is to develop and pilot test the MIAPP intervention. This pilot work will provide evidence of the feasibility/acceptability of the MIAPP intervention and research procedures that will be used to inform a future, larger study, as assessed by our ability to fully recruit the planned sample and deliver the intervention to the majority of those randomized to the intervention arm. The sample size of 40 for the pilot randomized controlled trial was chosen as we projected we could enroll and complete the study procedures and analyses within the available funding period. Although the sample size was not selected for the purpose of providing a fully-powered study, with our sample size of 40 we are nonetheless powered at 80% to detect some effects if they are large in size. For binary outcomes, power depends on the base rate of the outcome measured, and based on prior studies (38, 55), we anticipate that anywhere from 20% to 50% of participants in treatment as usual successfully linking to outpatient medications for OUD services post-discharge. For binary outcomes, including the primary outcome measure, our pilot study will be powered to detect intervention effect sizes of $RR \geq 1.89, 2.05, 2.40, \text{ or } 3.10$, if linkage rates for treatment as usual are 50%, 40%, 30%, or 20%, respectively.

For continuous outcomes (days of buprenorphine coverage, days of opioid or methamphetamine use), we will be powered to detect standardized effect sizes of Cohen's $d \geq 0.91$ with 40 participants.

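### Covariates for the primary model are chosen by between-arm baseline tests plus an undefined confounding judgement, so the risk ratio used for conclusions is not fixed in advance

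*Combined protocol and SAP*

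**What the plan says.** The opening paragraph of the Statistical Analysis Plan screens the baseline data by arm: "variables will be assessed for any differences between the two randomized arms using chi-square tests, t-tests, or the Mann-Whitney U test", the test depending on the distribution. It then gives a two-part rule for entry into the model: "Baseline variables that differ between the two arms and potentially confound tests of intervention effects will be included in analyses as covariates".

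Under Primary Outcome Analyses the rule becomes optional. The model compares the arms "while potentially controlling for any baseline variables that differ between the two groups as described above if they could confound the hypothesis test". The risk ratio from that model, adjusted or not, carries the result: "Results from the Poisson regression will be used for primary interpretation and conclusions". The difference in proportions is also reported.

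The plan does not say what p-value or size of difference counts as differing, how many variables will be tested, which are regarded as prognostic, or what makes a variable a potential confounder. Under Involvement of Human Subjects it says: "Patients will be assigned to one of two arms (20 per arm) using a stratified randomization procedure". The stratification factors are not named there, and the analysis sections do not put them in the model.

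**The concern.** In a properly randomised trial, any baseline difference between the arms is due to chance. A between-arm p-value describes the size of that chance imbalance relative to its standard error. It says nothing about whether the variable predicts linkage to treatment. With 20 per arm the screen can flag variables unrelated to the outcome and pass over modest imbalances in variables that matter.

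The second condition, that the variable could confound, would help if it were defined. It is not, and the primary model only potentially adjusts. Two competent analysts with the same data could report different primary risk ratios, and both would have followed the plan. The entry rule is worded for analyses in general, so it reaches the secondary outcomes too.

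At stake are the precision and reproducibility of the main estimate in a trial of 40, where precision is scarce and the result is meant to inform a larger study.

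**Working it through.** **Inputs from the documents.** 20 per arm; modified Poisson regression with robust standard errors; usual-care linkage of 50%, 40%, 30% or 20%, paired with detectable risk ratios of 1.89, 2.05, 2.40 and 3.10 at 80% power (Sample Size and Power).

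**Assumptions.** Two-sided 0.05 for the treatment test, inferred from the 95% interval. A 0.05 threshold for the baseline tests. k = 10 to 30 independent baseline variables; Research Material Obtained from Participants lists about ten domains but no count. Prognostic strength as stated below.

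**Step 1: the plan's own figures.** The plan gives no figure for its covariate rule, so the check starts from its power statement. With pooled variance,

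z = [(p1 − p0)√n − 1.96√(2p̄(1 − p̄))] / √(p0(1 − p0) + p1(1 − p1)).

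For p0 = 0.30 and RR 2.40: p1 = 0.72, p̄ = 0.51, n = 20, so z = (1.878 − 1.386)/0.642 = 0.77 and power is 77.9%. The 40% and 20% entries give 80.1% and 79.4%. The 50% entry gives 91.4%; it does not reproduce by this formula, but it errs on the conservative side and does not bear on this point.

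**Step 2: chance of flagging something.** P(at least one) = 1 − 0.95^k.
- k = 10: 40%, with 0.5 variables expected
- k = 20: 64%, with 1.0 expected
- k = 30: 79%, with 1.5 expected

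Correlated variables would lower these probabilities.

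**Step 3: effect on the estimate.** Simulated trials of 20 per arm (4,000 to 6,000 per scenario), k = 20 independent normal covariates, t-test screening at 0.05 and a probit outcome model. Where two variables are prognostic, each has a coefficient of 0.7 per SD. Tests alone means every flagged variable enters. Perfect filter means only flagged variables that are truly prognostic enter.

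| Scenario | Measure | Unadjusted | Tests alone | Perfect filter | Prespecified prognostic |
|---|---|---|---|---|---|
| RR 1, 40%, none prognostic | SD of log RR | 0.432 | 0.469 | 0.432 | none to include |
| same | rejection | 3.5% | 4.7% | 3.5% | none to include |
| RR 1, 40%, two prognostic | SD of log RR | 0.423 | 0.445 | 0.410 | 0.400 |
| same | rejection | 3.0% | 4.4% | 2.7% | 5.3% |
| RR 2.40, 30%, two prognostic | power | 74.7% | 69.1% | 75.3% | 85.1% |
| RR 2.05, 40%, two prognostic | power | 76.5% | 72.8% | 77.8% | 87.3% |
| RR 2.40, 30%, none prognostic | power | 75.8% | 69.7% | not run | none to include |

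- **Tests alone against unadjusted.** With no prognostic covariate the variance ratio is (0.469/0.432)² = 1.18, an 18% increase. The power losses above are 74.7 − 69.1 = 5.6, 76.5 − 72.8 = 3.7 and 75.8 − 69.7 = 6.1 points. A further scenario, 40% against 70% with none prognostic, gave 44% falling to 41%. The range is therefore roughly 3 to 6 points.
- **Fewer variables.** A rerun with k = 10 gave 75.4% to 73.2% and 77.0% to 75.3% with two prognostic variables, and 74.8% to 71.6% with none. The losses are 2.2, 1.7 and 3.2 points. Each power figure has a simulation error of about 0.7 points, so a fair statement is about 1 to 3 points.
- **Picking between models.** Under the null, claiming significance if either the unadjusted or the test-selected model reached it gave 5.4% to 5.5%.

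**Step 4: reading the prespecified column.** The 10-point gain at 30% and RR 2.40 (85.1 − 74.7 = 10.4) is mostly a benefit of prognostic adjustment over none. It should not be charged to the testing rule. Part of it also reflects test size: null rejection is 5.3% for the prespecified model and 3.0% for the unadjusted one. On the SD scale the gain is smaller: (0.400/0.423)² = 0.89, about 11% less variance.

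**The case against.** The strongest reply is that the plan does not enter every flagged variable. It also requires that the variable could confound, and a confounder must be related to the outcome. A reader might infer from the tests-alone results that the rule adds noise. The documents do not support that as a general statement: if the condition admitted only truly prognostic variables, the SD would fall slightly (0.410 against 0.423) and power would rise by about 1 point. The direction depends on how an undefined judgement is exercised. That part of the reply stands. It does not rescue the rule, because a model that turns on an undefined judgement is still not fixed in advance.

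A reader might also infer type I error inflation. The simulations do not show it: test-selected models rejected a true null in 4.4% to 4.7% of trials, and choosing the better of two models gave at most 5.5%.

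Nor do the documents show that covariates would be chosen with the outcome results in view. The written trigger is a baseline difference. The Statistical Analysis Plan does have the investigators reporting outcomes by unblinded arm to the monitoring board, and no separation from whoever chooses the covariates is described. That is a reason to fix the model early, not evidence of outcome-driven selection.

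Finally, this is a pilot whose sample size was set by feasibility, and the proportions by arm and their difference will be reported, so the raw comparison stays visible. That limits the consequence. It does not remove it: the plan states a primary hypothesis, draws conclusions from this model and says "with our sample size of 40 we are nonetheless powered at 80% to detect some effects if they are large in size".

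**Conclusion.** The point holds in a limited form. Between-arm baseline tests, joined to an undefined confounding judgement, decide which covariates enter the model whose risk ratio supports the conclusions. Nothing elsewhere in the document fixes that model.

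The size depends on how the rule is applied. It ranges from no material difference from the unadjusted analysis, if the confounding condition works perfectly, to a loss of roughly 3 to 6 power points if tests alone decide among 20 variables. In every case examined with prognostic covariates, the rule does worse than naming those covariates beforehand.

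That the covariate set is not prespecified rests on the text alone and is secure. The magnitudes rest on assumed values for the threshold, the number and independence of the variables, and their prognostic strength, and should be read as indicative. The harm is lost precision and analyst discretion, not false-positive inflation, and it is of moderate consequence in a pilot.

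**What to change.** Remove the between-arm baseline tests and the rule that admits variables because the arms differ. Present baseline data by arm descriptively.

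Before any arm-level data are seen, state the primary model: treatment plus the factor or factors used in the stratified randomisation. The Randomization section refers to the REDCap manual for procedural details. If the factors are recorded there, carry them into the analysis plan. Add at most one or two baseline variables that are already collected, named in the plan and chosen on expected prognostic value for linkage. Apply the same rule to the secondary outcomes. Report the unadjusted risk ratio alongside, and label any model adjusted for observed imbalance as a sensitivity analysis.

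The cost is a change of wording, with no new data, participants or procedures. There is a small statistical downside: a prespecified covariate that turns out not to be prognostic costs a little precision. In the simulation at 30% and RR 2.40, one such covariate moved power from 75.8% to 74.9%. Events may also be few (20% linkage among 20 usual-care participants is 0.20 × 20 = 4), which is a further reason to keep the list short.

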Research assessments will occur at baseline during hospitalization and 30 days after discharge from the hospital (“30-day follow-up”). Both assessments will ideally be in-person visits, with research staff administering assessments in an interview format. Point-of-care urine drug testing using Alere 14 Panel Drug Test iCup DX or equivalent will be administered at the 30-day follow-up visit only. Study data (including screening, assessment, urine drug testing results) will only be recorded for research purposes and will not be shared with clinical providers outside of the study team (unless there are imminent safety concerns). Participants will be reimbursed \$60 for the baseline visit and \$60 for the 30-day follow-up visit, plus another \$20 at the 30-day follow-up visit if a urine drug test is provided. This reimbursement for study participation will be provided to both study arms (MIAPP and control arm). At the 30-day follow-up visit, participants will return any study-provided smartphones, if utilized. Data extraction for secondary outcomes will occur after 180 days, which will encompass the 30-, 90-, and 180-day outcome timepoints we will report. These secondary outcomes will include outpatient visits/medications, hospital readmissions, and emergency department visits and will be obtained through partnership with WA State DSHS RDA. Data will be collected for patients who are enrolled in the pilot RCT (Aim 1), as well as for a larger, historical, observational cohort of HMC patients who initiated

treatment with buprenorphine between 2019 and 2021 (Aim 2). This will ensure the feasibility of collecting outcomes for a larger sample size and provide estimates of rates of healthcare utilization that can be used to power a larger clinical trial.

Eligibility

Inclusion Criteria:

- ≥ 18 years old
- Admitted to HMC on any inpatient service
- Initiated on sublingual buprenorphine for OUD while in the hospital or at the time of discharge and planning to continue outpatient
- Used methamphetamine within the past 30 days (any route of administration or frequency), per patient self-report at screening
- Willing to be randomized to MIAPP intervention or control condition
- Willing and able to use a smartphone (study can provide) and work with patient navigator
- Discharge setting does not preclude the use of video-DOT (i.e., nursing home, inpatient psychiatry, etc.)

Exclusion Criteria:

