Potential participants for the pilot study will be identified through the Addiction Consult Service (ACS). [name] (co-I) will work with the research staff and clinical team to help identify patients for the PN to approach for screening. Research staff (patient navigator and research coordinator) will also review the Addiction Consult Service's patient list and information in the electronic health record (EHR) to perform "pre-screening" where potentially eligible participants are identified. Potentially eligible patients will be approached by the research coordinator. If the patient is eligible and agrees to participate in the study, then the research staff will obtain written informed consent, conduct the baseline assessment, and then randomize the patient using a REDCap randomization module. The study will aim to enroll 40 patients for the Aim 1 pilot RCT (20 randomized to each condition).

Pre-Screening Methods

Pre-screening Electronic Health Record Charts of Potential Participants:

Potential participants for the pilot study will be identified through the Addiction Consult Service. [name] (co-I) will work with the research staff and clinical team to help identify patients for the PN to approach for screening. Research staff (patient navigator and research coordinator) will also review the Addiction Consult Service's patient list and information in the electronic health record (EHR) to perform "pre-screening" where potentially eligible participants are identified.

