Individuals who are eligible and enroll in the RCT will complete a baseline and a 30-day post-discharge study visit. Data to be collected at those visits include information on demographics, co-morbidities, current and past addiction treatment, medication adherence and knowledge, motivation and skills for adherence, current and past-year substance use, HIV risk behaviors, mental health symptoms, and satisfaction and trust in provider (both for physician and patient navigator). Urine drug testing will occur at the 30-day post-discharge visit using Alere 14 Panel Drug Test Cup iCup DX or equivalent multi-drug point-of-care test, and a fentanyl urine test strip. A review of medical records (electronic and faxed records from outside hospitals) will be conducted to record information on hospital readmissions and outpatient treatment for 90 and 180 days post-discharge. Assessment data will be collected directly onto netbook computers used by research assessors. We will utilize the Research Electronic Data Capture (REDCap) system through the University of Washington's Institute of Translational Health Services (ITHS). Hospital readmissions and Emergency Department visits within 90 and 180 days of discharge will be extracted by WA State DSHS RDA from statewide Medicaid claims data.

Consent Procedures

The informed consent process will be conducted by staff members trained in the ethical treatment of human subjects. This process involves presenting a detailed verbal description of the study as it is described on the printed, IRB-approved consent form. Subjects will be advised of the purpose of the research and will be asked to provide their verbal informed consent for screening. Answers will be recorded anonymously. Eligible subjects will then be informed of the details of the study and will provide written consent if they wish to participate. Research assessors will review the elements of consent with participants, including the purpose and duration of the study; a description of the study procedures; the risks, discomforts, and benefits; the procedures to ensure confidentiality (including use of unique, non-personally identifying ID numbers instead of names on research materials and maintenance of data in protected computer databases and locked filing cabinets in locked rooms); and that participation is voluntary and their decision whether or not to participate will not impact their clinical care in any way.

Risks to Human Subjects

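### Readmissions and ED visits are analysed only as any versus none; adding event counts and a rate ratio would cheaply improve an exploratory outcome

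*Combined protocol and SAP*

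**What the plan says.** Hypothesis (b) under Secondary Outcome Analyses is that the intervention arm will "have lower rates of readmissions to the hospital and emergency department visits within 90 days (exploratory"). The sentence that follows assigns these outcomes to "modified Poisson regression similar to those described above for binary outcomes (readmissions to hospital and emergency department"). The method referred to is the one under Primary Outcome Analyses, which compares the proportion of participants with an outcome and reports a risk ratio and a difference in proportions. No count model, person-time denominator or events-per-participant summary is specified for utilisation anywhere in the document.

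On the source, Research Material Obtained from Participants says that readmissions and ED visits "will be extracted by WA State DSHS RDA from statewide Medicaid claims data". On the purpose, Data Collection Overview says that collecting outcomes for the trial participants and the 2019-2021 cohort will "provide estimates of rates of healthcare utilization that can be used to power a larger clinical trial".

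On size, "The study will aim to enroll 40 patients for the Aim 1 pilot RCT (20 randomized to each condition"). No base rate, dispersion or target effect is stated for utilisation.

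**The concern.** Readmissions and ED visits can both recur within 90 days. Under an any-versus-none score, a participant with six ED visits and one with a single visit count the same, so a reduction in repeat visits is invisible unless it brings someone to zero. If visits are frequent, the any-event risk ratio sits much closer to 1 than the ratio of visit rates, and the comparison loses power.

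There is also a planning cost. A later trial powered on visit rates would need the mean and dispersion of the counts, and a proportion with any event supplies neither.

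**Working it through.** **Inputs.** 20 per arm (Screening and Recruitment). Two-sided 5% level: not stated, assumed from the 95% intervals ("We will also report the difference between proportions with a 95% confidence interval"). Visit mean and dispersion are not in the documents, so I assume negative binomial counts with control mean m per 90 days and variance m + φm². The main range is m = 1 to 3 and φ = 0.5 to 2; the range for k = 1/φ is the same. The rate ratio of 0.50 is an illustration.

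**The plan's own power figures.** Sample Size and Power states that "with our sample size of 40 we are nonetheless powered at 80% to detect some effects if they are large in size" and gives detectable RRs of 1.89, 2.05, 2.40 and 3.10 "if linkage rates for treatment as usual are 50%, 40%, 30%, or 20%, respectively". With the pooled normal formula for two proportions, power is 80.1% at 40%/2.05, 77.9% at 30%/2.40 and 79.4% at 20%/3.10, so these three are close to 80%. At 50%/1.89 it is 91.4% (detectable RR 1.79); that mismatch is a separate matter and does not affect this point. Read as reductions, the three that reproduce are 82% to 40% (RR 1/2.05 = 0.49), 72% to 30% (1/2.40 = 0.42) and 62% to 20% (1/3.10 = 0.32). On an any-event score, 80% power in these cases needs a risk ratio of about 0.5 or lower.

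**Step 1: what a halved visit rate looks like on the any-event score.** P(any) = 1 − (1 + φm)^(−1/φ).
- m = 1, φ = 0.5: 1 − 1.5^(−2) = 0.556; at m/2, 1 − 1.25^(−2) = 0.360; risk ratio 0.65.
- m = 2, φ = 1: 1 − 1/3 = 0.667; at m/2, 1 − 1/2 = 0.500; risk ratio 0.75.
- m = 3, φ = 2: 1 − 7^(−1/2) = 0.622; at m/2, 1 − 4^(−1/2) = 0.500; risk ratio 0.80.

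The main range therefore gives 0.65 to 0.80, an apparent reduction of 20-35%. Widening the assumptions to m = 0.25 to 4, including Poisson counts, widens the apparent reduction to 12-47%. At m = 0.5 it is 37-44%, already close to the true 50%.

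**Step 2: approximate power for rate ratio 0.50.** Any-event: pooled two-proportion formula. Counts: Φ(ln 2/√v − 1.96), with v = (1/m + φ)/20 + (2/m + φ)/20. For m = 2, φ = 1: v = 1.5/20 + 2/20 = 0.175, and 0.693/0.418 − 1.96 = −0.30, so power is 38%.

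| m | φ | P(any), control | P(any), halved rate | Risk ratio | Any-event power | Count power |
|---|---|---|---|---|---|---|
| 0.5 | 1 | 0.333 | 0.200 | 0.60 | 15.4% | 19.4% |
| 1 | 1 | 0.500 | 0.333 | 0.67 | 18.3% | 28.3% |
| 1 | 2 | 0.423 | 0.293 | 0.69 | 13.3% | 21.5% |
| 2 | 1 | 0.667 | 0.500 | 0.75 | 18.3% | 38.1% |
| 2 | 2 | 0.553 | 0.423 | 0.76 | 12.6% | 26.2% |

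**Step 3: the same comparison with test size controlled.** With 20 per arm, a robust Wald test on the log ratio of counts rejects 5-7% of the time under the null, while the same test on the any-event score rejects only about 2%. Setting those two side by side would credit counts with a gap that comes partly from the tests. With a permutation test on counts and a Pearson test on the any-event score, simulated power over the main range is about 16-52% against 11-26%. At m = 2, φ = 1 it is about 32% against 18%. The permutation figures are good to within a few points, since they depend on simulation error and the handling of ties.

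**Step 4: infrequent events.** At m = 0.5, the robust count test has 14-17% power and the Pearson test 13-19%. At means of 0.5 or less the count analysis has no advantage.

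**The case against.** The strongest reply is that hypothesis and analysis may already agree. Sample Size and Power uses 'linkage rates' for proportions. Read in that sense, hypothesis (b) is about the proportion readmitted or visiting the ED, and the next sentence analyses exactly that. This stands: a reader might infer a contradiction, but the text does not establish one.

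A reader might also infer that Data Collection Overview calls for a rate ratio. It asks for estimates of utilisation rates and names no effect measure. It draws them partly from the Aim 2 cohort, whose scoring is not described because the document covers Aim 1. Harm to the planning of the larger trial is therefore possible but not shown. Nor do the documents say that navigation would mainly reduce repeat visits, so the point cannot rest on that.

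Any-versus-none is also a conventional and robust score with 20 per arm, where a few heavy users can dominate a count model. That is a good reason to keep it, though not to omit the counts. Finally, the outcome is exploratory in a pilot whose sample size was not chosen for full power, and neither analysis reaches 80% power for a halved rate in the main range. This limits the importance of the point.

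**Conclusion.** The plan as written leaves repeat readmissions and ED visits out of the analysis and does not say whether 'rates' means events or people. This is an inefficient choice for an exploratory outcome and does not touch the primary conclusion.

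The size of the loss rests wholly on assumed visit rates. It is material if control participants average 1 to 3 visits per 90 days, where power on counts is higher in most of the range and about double at the upper means. It vanishes at 0.5 or fewer. The gain is thus more likely for ED visits than for readmissions, if readmissions are the rarer event. The apparent 20-35% reduction should not be quoted without the assumed means, because the documents supply none. Low severity: a cheap improvement worth considering.

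**What to change.** Under Secondary Outcome Analyses:
- State whether 'rates' means the proportion with any event, the number of events, or both.
- Keep the any-event risk ratio as planned.
- Add, for ED visits and readmissions separately, the number of events per person-90-days by arm and a rate ratio with 95% CI from a log-link count model (negative binomial, or Poisson with robust variance). Use log follow-up time as offset and small-sample robust or permutation inference. The offset matters because the Incarcerated Participants section provides for temporary withdrawal.
- Report the mean and dispersion of the counts for planning the larger trial.

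The cost is a few sentences and a few lines of code. Claims should yield counts without new data collection, but the documents do not say in what form the state agency will deliver them, so visit-level records or counts should be requested explicitly. Settling this before the 180-day extraction avoids choosing between definitions once results are known. The downside is small: a few heavy users can influence the rate ratio, so it should be read beside the any-event proportion.
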